4 STUDY POPULATION

4.1 Population

30 male and female subjects, (minimum age 18 years old) suffering from chronic post-surgical pain, for a minimum of 6 months, whom are routinely scheduled for a DRG stimulation will be recruited by the study site and Investigators for inclusion in the cohort.

Subjects must meet all of the inclusion and none of the exclusion criteria to be enrolled in the post market observational cohort study. Subjects will read and sign an informed consent prior to the treatment. Subjects will be recruited from the site's existing patient population and through new patient contacts as normally progresses in standard clinical practice.

4.2 Inclusion criteria

- 1) Subject is at least 18 years old
- 2) Subject is able and willing to comply with the follow-up schedule and protocol
- 3) Chronic post surgical pain for at least 6 months
- 4) Failed conservative treatments for chronic pain including but not limited to pharmacological therapy, physical therapy and interventional pain procedures for chronic pain
- 5) Minimum baseline pain rating of 60 mm on the VAS in the primary region of pain
- 6) Subject is able to provide written informed consent
- 7) Pain medication dosage has been stable for at least 30 days
- 8) Patient has been included for implantation according to standard criteria from the Dutch Neuromodulation Society

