3 STUDY DESIGN

This study is a prospective, single-arm, multi-centre post market observational cohort study, designed to assess the clinical effects of the commercially available Spinal Modulation DRG Neurostimulator System, in the management of chronic post-surgical pain. Subjects that are routinely scheduled to receive DRG stimulation will be asked to participate in this observational cohort study. They will be screened based upon the standard inclusion and exclusion criteria for neuromodulation in The Netherlands. Informed Consent will be obtained and they will then be enrolled into the cohort. Baseline parameters will then be measured in subjects using standard questionnaires and according to standard neuromodulation practice.

The study consists of two distinct phases in which the patients are asked to complete questionnaires, corresponding to the two-phase treatment process: 1) Temporary Trial Stimulation, and, 2) Implantable Stimulation (Figure 1).

Subjects will “trial” an external neurostimulator system for a period of time in line with standard hospital practices but no longer than 30 days (phase 1). If subjects experience sufficient pain relief in their primary area of pain, according to current neuromodulation guidelines, they will be eligible to proceed with the second phase of the treatment. If the

eligible subjects agree to move forward into Phase 2, they will undergo another surgical procedure in which the Spinal Modulation implantable Neurostimulator will be implanted. Subjects will be seen for follow-up at 1 week, 4 weeks, 3 months, 6 months, 12 months and 24 months following implantation (Figure 1). The site can contact the subjects telephonically for a follow-up at 8 weeks, 9 months and 18 months if desired (optional).

[figure not shown]

Figure 1. Basic design and follow-up schedule for subjects enrolled into the post-market observational cohort study. Subjects who have consented and been enrolled will undergo a two-phase process for advancement through the cohort. A detailed follow-up schedule can be found in the *Methods* section.

Protocol Phase 1 – Temporary Trial Neurostimulation

Following consent and entry into the post market observational cohort study, baseline parameters will be measured by means of the standard evaluation questionnaires used in The Netherlands

Protocol Phase 2 – Implantable Stimulation and Follow Up

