7.3 Study procedures

During the post market observational cohort study, data will be collected on Case Report Forms (CRFs). A copy of the CRFs will be provided for review.

Subject Screening and baseline

Subjects presenting with chronic post-surgical pain for at least 6 months will be screened for possible entry into the post market observational cohort study. Subjects will be screened according to the Inclusion/Exclusion criteria and only subjects meeting all Inclusion criteria and none of the Exclusion criteria will be enrolled. The post market observational cohort study will be explained to all subjects and subjects will provide informed consent prior to any data collection for the study. Subjects will be allowed to discuss their participation in the cohort with the study physician, clinical staff, family, friends and personal or external physician.

Following subject screening and acquisition of Informed Consent, subjects will undergo a baseline assessment to collect clinical data prior to lead implantation and stimulation.

Trial Stimulation Lead Implant Procedure

Following collection of baseline measurements, subjects will begin Phase 1 of the two-step treatment process.

End of TNS Trial Phase

At the end of the Trial Phase, pain relief will be assessed to determine whether a subject should receive an INS implant. The duration of the trial will be at the investigators discretion and in line with current clinical practice. This may be done in the theatre during the TNS procedure or after an extended trial period but should be no longer than 30 days.

INS Implant Procedure

Eligible subjects willing to continue with the implant will undergo surgery to implant the internal neurostimulator (INS). If the subdural leads are removed during the trial period, new leads will also be implanted at this time (see Physician Implant Manual for detailed information regarding the procedure). Each subject will receive a hand-held Patient Programmer that can be used to adjust stimulation amplitude as needed.

Regular Follow-ups

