9 STATISTICAL ANALYSIS

9.1 Descriptive statistics

Descriptive statistics will be used to evaluate the means and standard deviations of data collected as well as to compute the changes in the outcomes compared to baseline.

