9.2 Analysis

Univariate, multivariate and covariate statistical analyses will be conducted as appropriate to statistically tests for both primary and secondary outcomes. Statistical analyses will be conducted utilizing SAS and/or SPSS statistical software. *Post-hoc* power analyses will also accompany the omnibus testing and *post-hoc* analyses determining differences

between baseline and treatment means. All levels of significance will be deemed to occur at $p<0.05$.

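### The plan lets one VAS reading both qualify the patient (60 mm or more) and serve as the reference for change, so regression to the mean may be counted as pain relief

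*Combined protocol and SAP*

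**What the plan says.** All references are to the combined protocol and SAP.

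- **Entry cut-off.** Section 4.2, criterion 5: "Minimum baseline pain rating of 60 mm on the VAS in the primary region of pain". The cut-off is on the scale of the primary outcome (section 2), and the rating is itself called baseline.
- **Reference for change.** Section 9.1 will "compute the changes in the outcomes compared to baseline". Section 9.2 tests differences "between baseline and treatment means. All levels of significance will be deemed to occur at" the 0.05 level. Neither section says which pre-treatment VAS is meant.
- **Design.** Sections 3 and 7.2: one arm, no randomisation, no blinding.
- **Order of events.** Section 4.1: "Subjects must meet all of the inclusion and none of the exclusion criteria to be enrolled". Section 3, after screening, consent and enrolment: "Baseline parameters will then be measured in subjects using standard questionnaires and according to standard neuromodulation practice". Section 7.3: "Following subject screening and acquisition of Informed Consent, subjects will undergo a baseline assessment". Section 7.3 also requires consent before any study data are collected.
- **Schedule.** Appendix A, Table 1 marks the inclusion/exclusion form (CRF-1) and the pain measurement (CRF-7) at Baseline. Its header has no screening visit. The table is broken in the text available, so only the marks and column names that are present are used here.

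**The concern.** A patient's VAS on a given day is a stable level plus rating error. Admitting only ratings at or above a cut-off keeps some patients whose rating was high by chance. When they rate again, the error is drawn afresh and the mean falls, treatment or not. If the qualifying rating is also the reference for change, that fall enters the primary outcome as pain relief. A control arm would show the same fall and cancel it, but this study has none.

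The wording makes this possible. Criterion 5 needs a baseline rating before a patient can be enrolled, while section 3 measures baseline after enrolment. One site could use a rating from routine care for criterion 5 and take a new one as the reference. Another could take a single rating after consent and use it for both. Both would report change from baseline, but only the second would carry the bias.

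**Working it through.** **Step 1. Is there a stated figure to reproduce?** No. Section 4.4 says that no sample size calculation is needed and aims for 30 subjects. The documents give no VAS mean, SD or reliability.

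**Step 2. Inputs.**
- From the documents: cut-off 60 mm (section 4.2).
- Assumed: candidate mean μ, SD σ and test-retest reliability ρ. The central case is μ = 70 mm, σ = 15 to 20 mm, ρ = 0.7. The wider range is μ = 60 to 75 mm, σ = 15 to 20 mm, ρ = 0.5 to 0.9. A high-mean case uses μ = 80 mm.
- Left out: treatment effect and trial-phase selection.

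**Step 3. Formula.** With a = (60 − μ)/σ and λ = φ(a)/[1 − Φ(a)], where φ and Φ are the standard normal density and distribution function:
- mean qualifying rating = μ + σλ
- expected fall from the qualifying rating to a later rating = σ(1 − ρ)λ

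**Step 4. One reading does both jobs.**

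| μ | σ | ρ | a | λ | Spurious fall (mm) |
|---|---|---|---|---|---|
| 70 | 15 | 0.7 | −0.667 | 0.427 | 15 × 0.3 × 0.427 = 1.9 |
| 70 | 20 | 0.7 | −0.500 | 0.509 | 20 × 0.3 × 0.509 = 3.1 |
| 65 | 20 | 0.7 | −0.250 | 0.646 | 20 × 0.3 × 0.646 = 3.9 |
| 80 | 15 | 0.7 | −1.333 | 0.181 | 15 × 0.3 × 0.181 = 0.8 |
| 80 | 10 | 0.9 | −2.000 | 0.055 | 10 × 0.1 × 0.055 = 0.06 |

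Over the wider range the fall runs from 0.4 mm (75/15/0.9) to 8.0 mm (60/20/0.5). The figure of under 1 mm at mean 80 depends on the SD: with σ = 20 and ρ = 0.7, 20 × 0.3 × 0.288 = 1.7 mm. Simulation with ratings clipped to 0–100 agrees with the formula to within about 0.1 mm.

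**Step 5. Scale.** In the central case the mean qualifying rating is 70 + 15 × 0.427 = 76.4 mm, or 70 + 20 × 0.509 = 80.2 mm. The spurious fall is 1.9/76.4 = 2.5% or 3.1/80.2 = 3.8% of it. Halving the pain from there would be a fall of 38 to 40 mm.

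**Step 6. A separate reference.** If a second, independent pre-treatment rating is the reference, the simulated fall with no effect is about 0 mm (−0.09 to +0.07 mm over the wider range). In the central case about 13% (σ = 15) to 16% (σ = 20) of qualifying patients have a reference below 60 mm, which is 4 to 5 of 30.

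**Step 7. When a separate reference is not enough.** If ratings close in time correlate more strongly than ratings far apart, the remaining fall is σλ(r₁ − r₂). Here r₁ is the correlation of the eligibility rating with the reference, and r₂ its correlation with follow-up. Assumed gaps of 0.1 to 0.2 give 15 × 0.427 × 0.1 = 0.6 mm to 20 × 0.509 × 0.2 = 2.0 mm.

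**The case against.** **The sequence already separates the readings.** Sections 3, 4.1 and 7.3 put screening before the baseline assessment, so eligibility may be settled on an earlier routine-care rating. This stands as far as it goes. A reader might infer from criterion 5 that the qualifying rating certainly is the reference, and the documents do not support that. Equally, nothing in them says that the two differ. Criterion 5 calls its own rating baseline, no eligibility VAS is described, and CRF-1 and CRF-7 are both marked at Baseline.

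**The population is stable.** Stable medication for 30 days (section 4.2) and exclusion of a changing pain condition (section 4.3) limit real fluctuation. They do not remove rating error.

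**The size is unknown and may be negligible.** This stands. If patients already scheduled for implantation rate well above 60 mm, the effect is close to zero.

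**The consequences could be put more strongly.** A reader might infer an inflated false-positive rate for the p < 0.05 tests, or a larger bias because "pain relief will be assessed to determine whether a subject should receive an INS implant" (section 7.3). Neither can be given a reliable figure. A no-effect error rate that ignores the trial-phase decision describes a study that this plan does not run. A calculation that includes the decision needs a success threshold and a comparison rating, and the documents give neither.

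**Little hangs on it.** The study is observational, with no success threshold, and placebo response and natural course are uncontrolled in any case. That limits the weight of the point. But the change score is the primary result, it is to be published (section 11.5), and this part of the bias is cheap to avoid.

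**Conclusion.** The point holds as a conditional one. The plan allows a single VAS reading both to admit the patient and to serve as the reference for change. If that happens, regression to the mean is reported as pain relief. With assumed inputs the amount is about 2 to 3 mm in the central case, about 4 mm at mean 65 mm with SD 20, and under 1 mm at mean 80 mm with SD 15 or less. These figures leave out trial-phase selection, assume independent rating errors, and rest on no value from the documents beyond the 60 mm cut-off.

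A reader might conclude that the reported relief would be largely artefact. The figures do not support this: even the top of the wider assumed range, 8.0 mm, is about a tenth of its mean qualifying rating of 76.0 mm. This is a modest, avoidable bias and an improvement to consider. It is not a flaw that invalidates the study.

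**What to change.** - **Section 4.2.** State that the rating of 60 mm or more is the screening or routine-care rating and is used for eligibility only. Record its date and source on CRF-1 after consent, which keeps to the rule in section 7.3 on consent before data collection.
- **Section 9.1.** Define the separate post-consent baseline VAS (CRF-7), not used for eligibility, as the reference for all VAS change scores. Report change from the eligibility rating as a sensitivity analysis.
- **If no earlier rating exists.** Record one further VAS before lead placement, so that the rating used for eligibility is not also the reference.
- **Analysis set.** State that patients stay in the analysis when the reference VAS is below 60 mm (about 13 to 16% in the central assumed case).
- **Limitations to state.** Selection through the trial-phase decision, falling correlation over 24 months, placebo response and natural course all remain.

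**Cost.** Where a routine-care rating exists, the change is wording in two sections and a date-and-source entry on CRF-1. Where none exists, it is one extra VAS, and the Summary's statement that participation adds no risk or burden must be checked against it. The reported change may be slightly smaller. No treatment decision is altered.

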4.3 Exclusion criteria

- 1) Female subject of childbearing potential is pregnant/nursing, plans to become pregnant or is unwilling to use approved birth control
- 2) Escalating or changing pain condition within the past month as evidenced by investigator examination
- 3) Subject has had corticosteroid therapy at an intended site of stimulation within the past 30 days
- 4) Subject has had radiofrequency treatment of an intended target DRG within the past 3 months
- 5) Subject currently has an active implantable device including ICD, pacemaker, spinal cord stimulator or intrathecal drug pump
- 6) Subject is unable to operate the device
- 7) Subjects with indwelling devices that may pose an increased risk of infection

- 8) Subjects currently has an active infection
- 9) Subject has participated in another clinical investigation within 30 days
- 10) Subject has a coagulation disorder or uses anticoagulants that, in the opinion of the investigator, precludes participation
- 11) Subject has been diagnosed with cancer in the past 2 years.
- 12) Patient has no other exclusion criteria according to standard criteria from the Dutch Neuromodulation Society

4.4 Sample size calculation

As this is a post market observational cohort study, no sample size calculations are necessary. We aim to enrol 30 subjects in this cohort.

5 TREATMENT OF SUBJECTS

5.1 Treatment

The *Physician Implant Manual* provides a detailed description of the implant and surgical technique. Following informed consent and baseline measurements, subjects will begin phase one of a two-phase treatment process. Phase 1 is the Trial Phase and consists of percutaneously implanting neurostimulator leads into the epidural space and connecting them to an external neurostimulator. This system is then “trialed” for a period of time not to exceed 30 days. If the subject achieves sufficient pain relief in their primary area of pain according to Dutch Neuromodulation criteria during the trial phase, they will progress to Phase 2, the implantation phase. In this phase, the implanted leads will be connected to an implantable neurostimulator. The entire system is implanted under the skin for the duration of device use. The therapy is fully reversible and the leads and device can be removed through a similar procedure.

5.2 Use of co-intervention

Subjects may continue using medication for the treatment of their pain condition. The prescription of medication for pain will be dictated by the Pain Specialist according to standard care.

6 Description of the Device

6.1 Name and description of Neurostimulator System

The Spinal Modulation Neurostimulator System consists of the following components:

- Trial Neurostimulator
- Implantable Neurostimulator
- Trial Lead Kit
- Implant Lead Kit
- Connector Cable Kit
- Tunneling Tool Kit
- Clinical Programmer
- Patient Programmer
- Auxillary Magnet Kit
- Programmer Charger Kit
- Programmer Carrying case
- Lead Accessories Kit
- 22 cm Small Curve Delivery Sheath Kit
- 22 cm Big Curve Delivery Sheath Kit
- Lead Extension Kit

A detailed description of the components can be found in the physician implant manual.

On 16 November 2011, BSI granted Spinal Modulation, Inc. a CE mark for the Spinal Modulation DRG Neurostimulator System for the Management of Chronic Intractable Pain (CE 567069). The system has been notified to the CIBG in the Netherlands on 24 November 2011.

6.2 Summary of known and potential risks and benefits

A summary of the known and potential risks and benefits can be found in the accompanying manuals that are included in the packaging of the components. The general risks associated with the Spinal Modulation DRG Neurostimulator System are similar to those associated with other currently approved Spinal Cord Stimulator systems. Possible risks to the subjects include both device and procedural based risks. The most common side effects and risks are:

- Pain (where the needle is to be inserted)
- Pain caused by understimulation due to lead migration
- Pain over the implantable neurostimulator site (only applicable in Phase 2)
- Escalating pain
- Bleeding (where the needle has been inserted)
- Headache
- Infection
- Localized collection of serous (clear) fluid at injection site
- Discomfort during the treatment
- Allergic or rejection response to implant materials
- Constant pain at the lead site
- Stimulation of the chest wall
- Lead migration (movement) and/or local skin breakage
- Weakness
- Clumsiness
- Numbness
- Temporary muscle activation

Very rare risks and side effects include:

- Cerebral Spinal Fluid (CSF) leakage
- Tissue damage
- Nerve damage
- Spinal cord compression
- Swelling
- Paralysis
- Hematoma
- Seroma
- Sensory loss
- Skin erosion around the INS or leads
- Battery failure and/or battery leakage
- Lead breakage requiring replacement of the lead
- Hardware malfunction requiring replacement of the neurostimulator
- Pain from a non-injurious stimulus to the skin (allodynia)
- An exaggerated sense of pain (hyperesthesia)

6.3 Device utilization

A detailed description of device utilization can be found in the Physician Implant Manual. All investigators involved in the study have been trained on the use of the Spinal Modulation DRG Neurostimulator System and already have experience in the use of the commercially available products.

6.4 Devices

The devices that will be used in the post market observational cohort study are commercially available products and will be bought and paid for according to the standard hospital system. Serial and lot numbers of the products used will be added to the patient files to document and identify the devices.

7 Methods

7.1 Assessments

During the scheduled follow-ups the following measurements will be performed. Table 1 in appendix A gives a detailed description of the measurements per follow-up.

- Pain relief (VAS)
- Quality of life (EQ-5D)
- Physical functioning (BPI)
- Pain distribution
- Paresthesia Distribution
- Sleep quality
- Subject satisfaction
- Device safety
- Device settings and procedural information

7.2 Randomisation, blinding and treatment allocation

As this is an observational study, no randomisation or blinding will occur. All subjects will be receiving the Spinal Modulation DRG Neurostimulator System and data will be collected at each follow-up time point.

7.3 Study procedures

During the post market observational cohort study, data will be collected on Case Report Forms (CRFs). A copy of the CRFs will be provided for review.

Subject Screening and baseline

Subjects presenting with chronic post-surgical pain for at least 6 months will be screened for possible entry into the post market observational cohort study. Subjects will be screened according to the Inclusion/Exclusion criteria and only subjects meeting all Inclusion criteria and none of the Exclusion criteria will be enrolled. The post market observational cohort study will be explained to all subjects and subjects will provide informed consent prior to any data collection for the study. Subjects will be allowed to discuss their participation in the cohort with the study physician, clinical staff, family, friends and personal or external physician.

Following subject screening and acquisition of Informed Consent, subjects will undergo a baseline assessment to collect clinical data prior to lead implantation and stimulation.

Trial Stimulation Lead Implant Procedure

Following collection of baseline measurements, subjects will begin Phase 1 of the two-step treatment process.

End of TNS Trial Phase

At the end of the Trial Phase, pain relief will be assessed to determine whether a subject should receive an INS implant. The duration of the trial will be at the investigators discretion and in line with current clinical practice. This may be done in the theatre during the TNS procedure or after an extended trial period but should be no longer than 30 days.

INS Implant Procedure

Eligible subjects willing to continue with the implant will undergo surgery to implant the internal neurostimulator (INS). If the subdural leads are removed during the trial period, new leads will also be implanted at this time (see Physician Implant Manual for detailed information regarding the procedure). Each subject will receive a hand-held Patient Programmer that can be used to adjust stimulation amplitude as needed.

Regular Follow-ups

Subjects will be followed according to the standard follow-up schedule for 24-months following implant at regular intervals: 1-week (± 5 days), 4 weeks (± 1 week), 3 month (± 2 weeks), 6 month (± 2 weeks), 12 months (± 2 weeks) and 24 months (± 2 weeks). The given time-windows are advisable and therefore visits outside the time windows will not be seen as a protocol deviation. If desired, the Investigators may contact the subjects telephonically for evaluations at 8-weeks, 9-months and 18 months post-implant.

Prior to completing the required measurements, the subject will have his/her stimulator reprogrammed if needed or applicable.

24-month follow-up (Study Exit)

The study will end 24 months following INS implantation. At this visit, the regular follow-up assessments as outlined in appendix A will be acquired and a trial exit form will be completed.

Following completion of the study, subjects will continue to use the Spinal Modulation DRG Neurostimulator System. They will be monitored by their physician in accordance with standard medical procedures.

Interim Programming/Revision/Replacement/Explant (if necessary)

During the course of the cohort, subjects will have the option to return to the study site at any time to have their neurostimulator re-programmed to achieve maximal benefit. If any part of the Spinal Modulation Neurostimulator System becomes dysfunctional or requires adjustment following implantation, the patient will come to the site for analysis of the problem (interim visit). In appendix A, the assessments are listed for an interim visit and a revision (if applicable).

